WHO	World Health Organization

PROTOCOL SUMMARY

- Title:** Natural History of Infection Caused by BK Virus (and other Opportunistic Viral Pathogens) in Renal and Renal-Pancreas Transplant Recipients
- Phase:** Not Applicable (Natural History Study)
- Study Population:** Male and female renal or renal-pancreas transplant recipients at risk for BK virus infection
- Sample Size:** Approximately 450 subjects will be enrolled for screening for BK viremia (15% over-enrollment allowed, to a maximum of 518 screened subjects) to allow identification of approximately 40 (to a maximum of 60) subjects with viremia.
- Number of Sites:** Approximately 6
- Study Duration:** 3 years
- Subject Participation Duration:** Maximum of 24 months
- Objectives:**
- Primary Objectives:**
- To establish the natural history of BK viremia in a multicenter population of renal and renal/pancreas transplant patients, to include incidence, time to onset, duration, and quantitation of viral load;
 - To assess associations between BK viremia and decline in GFR in renal transplant recipients.
- Secondary Objectives:**
- To define the donor and recipient-related risk factors for BK viremia and BKVN in a multicenter population of renal and renal-pancreas transplant patients;
 - To define the frequency of clinical outcomes that are potentially related to BKV infection.
- Tertiary (Exploratory) Objectives:**
- To compare quantitative measurements of BKV DNA by PCR in plasma and (when appropriate) in urine, in order to determine biologic significance;
 - To assess plasma for evidence of other opportunistic viral pathogens, including CMV, EBV, HHV-6, and adenovirus;
 - To assess urine for evidence of other opportunistic viral pathogens, including CMV and adenovirus;

- To compare quantitative BKV PCR results from each site (local or reference laboratory) with matched results from the Central Unit laboratory;
- To explore the potential of biomarkers of tubular injury for predicting increased risk of BKVN;

[figure not shown]
Description of Study Design:

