The primary objective is to define the natural history of BK viremia. In order to understand the natural history of infection, we will measure the time (days post-transplant) to the development of BK viremia and its correlation with progression to end-organ disease (BKVN or BK hemorrhagic cystitis). Data from this prospective monitoring will allow for the identification of the types of high-risk patients who might benefit from future studies of therapeutic interventions for BKV infection (when effective therapy becomes available). This will be accomplished by serial quantitative BK DNA measurements in blood (plasma), assayed by polymerase chain reaction (PCR). Phases of the study can be summarized as follows:

- Subject identification and informed consent. Informed consent should be obtained early in the peri-transplant period (between 7 days pre-transplantation [T-7d] and 100 days post-transplantation [T+100 d]).
- Prospective screening for BK viremia. Enrollment and initiation of specimen collection should begin no sooner than 4 weeks after transplantation. Enrollment cannot occur later than 100 days after transplantation. Subjects will be screened (collection of blood and urine for laboratory studies, including BK PCR) approximately monthly for 6 months (timed from the date of transplantation), then every other month for 6 months. For those subjects who remain BKV-negative, screening will terminate approximately 12 months from the date of transplantation.
- Intensive sampling of subjects identified with BK viremia. Subjects identified with qualifying viremia will be sampled approximately every two weeks until resolution of viremia (defined as PCR negative, or <1000 copies/ml).
Note: Patients who did not participate in the prospective screening phase but are identified with BK viremia by standard-of-care testing may be enrolled, as long as they are still within 100 days of transplantation.
- Post-viremia follow-up. Following resolution of viremia, subjects will be sampled (collection of blood and urine) approximately monthly for 6 months (unless another termination event occurs sooner).

SCHEMATIC OF STUDY DESIGN

DMID Protocol # 11-0071 Active Screening/Natural History Phase

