3.2.2. Secondary endpoints

- Timing of onset of BK viremia (number of days post-transplant)

- Duration of BK viremia
- Incidence of BKVN in the study population
- Dynamics of quantitative measurements of BK viremia over time
- Frequency of donor and recipient-related risk factors for BV viremia, including:
 - a. Donor-derived factors:
 - i. Deceased donor – Standard criteria donor (SCD), Donor after cardiac death (DCD), Expanded criteria donor (ECD)
 - ii. Living donor – related donor or unrelated donor
 - iii. ABO incompatibility
 - iv. Total HLA mismatches
 - v. HLA C7 status
 - vi. Race/ethnicity
 - vii. Sex
 - b. Recipient-derived factors:
 - i. Delayed graft function (DGF), defined as use of dialysis within 7 days of the transplant
 - ii. Cold ischemia time (CIT)
 - iii. Warm ischemia time (WIT)
 - iv. Use of stents
 - v. HLA C7 status
 - vi. Type/intensity of immunosuppression, including corticosteroids
 - vii. Acute rejection
 - viii. Age
 - ix. Race/ethnicity
 - x. Sex
- Frequency of clinical outcomes that are potentially related to BKV infection, including:
 - a. subject death,
 - b. loss of graft function as defined by GFR <10 mL/min/1.73 m²
 - c. development of urinary outlet obstruction
 - d. development of gross hematuria
 - e. development of lymphocele
 - f. acute rejection
 - g. initiation of dialysis
 - h. re-transplantation
 - i. renal biopsies

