4.2. Prospective Screening Phase

Approximately 450 subjects will be screened for BK viremia (15% over-enrollment allowed, to a maximum of 518 screened subjects). During the screening phase, subjects will submit blood (plasma) for quantitative measurement of BKV DNA approximately every 4 weeks, ± 7 days, for 6 months (timed from the date of transplantation) and then approximately every 8 weeks, ± 14 days for 6 months. Also, urine specimens will be collected at each visit and stored for subsequent testing. During the screening phase, the specified intervals between sample collections should be followed as closely as possible, but may vary with subject availability. If qualifying BK viremia is not detected, surveillance will terminate approximately 12 months after the date of transplantation (or when another study termination endpoint is reached, whichever occurs sooner).

NOTE: BKV PCR results of $\geq 10,000$ from the study central laboratory, the site laboratory, or a reference laboratory are acceptable to qualify the patient for inclusion in the Intensive Monitoring Phase of the study.

NOTE: Non-study patients who are determined to have a qualifying blood BK viral load ($\geq 10,000$ copies/ml) during the course of routine clinical care (i.e., patients not consented and not identified by prospective screening/surveillance) will also be eligible for enrollment directly into the intensive monitoring surveillance phase after providing consent as long as they remain within the window of ≤ 100 days following transplantation.

Subjects will remain in the screening/surveillance phase: 1) for 12 months post-transplantation; 2) until qualifying BK viremia is documented; 3) until renal graft failure, re-transplantation, and/or initiation of chronic dialysis occurs; 4) death; 5) until subject decides to terminate participation; 6) until the investigator decides that the subject should terminate participation; or 7) until the study closes (whichever occurs first). Reason for termination of participation in the study will be documented.

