4.3. Intensive Sampling Phase

Approximately 40 viremic subjects (up to a maximum of 60) will be asked to participate in more intensive sampling. Those subjects in whom BK viremia is identified (by PCR result demonstrating BK DNA $\geq 10,000$ copies/ml) will be shifted to a more intensive sampling schedule. A review of the informed consent will be initiated by the research staff to confirm the subject's continued willingness and ability to participate in the intensive monitoring phase until resolution of viremia or until another discontinuation event occurs.

Blood and urine specimen collection will occur every 2 weeks, \pm 7 days, until the BK viremia has resolved (or another study termination endpoint is reached). Resolution of BK viremia is defined as PCR becoming negative (or viral load <1000 copies/ml). Start and stop dates for the Intensive Sampling Phase will be defined by the date that the qualifying (initial positive and subsequent negative) blood samples were drawn.

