4.4. Post-Viremia Follow-Up

Following resolution of viremia, subjects will return to the previous sampling schedule (approximately every 4 weeks, \pm 14 days) for an additional 6 months (or until another study termination endpoint is reached, whichever occurs sooner). The first follow-up visit should occur approximately 4 weeks after the BK viral load was documented to be negative.

Subjects will remain in the post-viremia follow-up phase: 1). for 6 months following resolution of the BK viremia; 2). until another study termination endpoint is reached; 3). until death; 4). until they decided to terminate participation; 5). until the investigator decides that the subject should terminate participation; or 6). until the study closes (whichever occurs first). Reason for termination of study participation will be documented.

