5. STUDY POPULATION

5.1. Study Population Selection

All adult renal or renal-pancreas transplant patients who meet protocol inclusion/exclusion criteria are eligible for participation in this study.

In an effort to capture subjects early in the course of the evolving BK infection and avoid subjects who have already developed evidence of BKVN, this protocol will emphasize consent in the early peri-transplant period. Patients may be consented while hospitalized pre-transplantation (as early as 7 days prior to transplantation) or at an outpatient follow-up visit (as late as 100 days post-transplantation). The study enrollment visit and initial collection of protocol-defined specimens will take place between 4 weeks and 100 days following renal or renal/pancreas transplantation.

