8.4.2. Secondary Endpoints

The distribution of the time to onset and duration of BKV viremia will be estimated using survival analysis methods such as Kaplan-Meier estimator for a single group. This will provide estimates of the median time to onset or median duration of BKV viremia. To compare different groups and/or determine risk factors, we will use Cox proportional hazard regression model if the proportional hazards assumption is found to be reasonable. Otherwise, we will consider using parametric survival regression models (in particular, accelerated failure time model). Parametric regression models are useful especially in cases where sample sizes are small or when the percent censored is high. This will also be the tool of preference if there will be left-censored subjects, i.e., subjects who at enrollment show evidence of BK viremia. Cox model cannot handle left-censored data.

As with the BKV viremia, incidence of BKVN will be estimated using a 95% confidence interval for single proportion. We will utilize logistic regression to compare groups, or adjust for covariates or determine risk factor.

To investigate the change in the quantitative BK viremia over time and how it is associated with important factors such as the use of immunosuppressive therapy and recipient's demographic and clinical characteristics, we will again use mixed regression modeling for repeated measures.

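### BKVN incidence and risk factors are analysed without time at risk, although viremia status decides how long each subject is observed, and the clinical outcomes have no stated estimator

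*Combined protocol and SAP*

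**What the plan says.** **Observation time.** The enrollment visit falls "between 4 weeks and 100 days following renal or renal/pancreas transplantation" (5.1). For the screening phase, section 4.2 states: "If qualifying BK viremia is not detected, surveillance will terminate approximately 12 months after the date of transplantation". The Protocol Summary and Appendix A-1 agree. A subject with qualifying viremia moves to two-weekly sampling until viral load is negative or below 1000 copies/ml (4.3). That subject then stays "for 6 months following resolution of the BK viremia" (4.4), unless another termination event comes first. The Protocol Summary caps participation: "Maximum of 24 months". No rule keeps a viremic subject under observation until at least Month 12.

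**Analysis.** As with viremia, "incidence of BKVN will be estimated using a 95% confidence interval for single proportion" (8.4.2). Risk factors and group comparisons for BKVN use logistic regression (8.4.1, 8.4.2). No horizon, censoring rule, offset or person-time is given. Section 3.2.2 also lists "Frequency of clinical outcomes that are potentially related to BKV infection, including" death, graft loss, acute rejection, dialysis and biopsies, but section 8.4 assigns these no estimator. Survival methods are planned for onset and duration of viremia (8.4.2) and for one exploratory question, time to BKVN against immunosuppression (8.4.3).

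**The concern.** A proportion needs a common period, or its denominator has no clear meaning. Here the period is set by the course of the infection under study. Someone who clears viremia early and leaves at Month 10 is a non-case on the same footing as someone followed without BKVN for two years.

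This affects three things:
- The BKVN incidence is not a risk to Month 12, to Month 24 or to any other time.
- A BKVN odds ratio can partly reflect length of observation. Type and intensity of immunosuppression is a listed factor, and section 2.1.1 reports that some BKVN patients appear to clear virus after it is reduced. A factor that changes time to clearance also changes time observed.
- If the 3.2.2 outcomes were tabulated by viremia status, events after about Month 12 could be recorded only in subjects who had become viremic, and some other viremic subjects would have left before Month 12.

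**Working it through.** **The plan's own figures.** The documents give no figure for BKVN or clinical outcomes by viremia status. The nearest is the GFR power in 8.2.1. With 40 and 410 subjects, SD 10.9 and difference 5.9, a two-sided 5% t-test on 448 df has power 0.903, which agrees with the stated 90%. The point does not rest on this figure; only the 40/410 split is used below.

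**Step 1: when observation ends.** Without viremia, exit is at Month 12. Observed time is (365 − 28)/30.44 = 11.1 months for enrollment at day 28, and (365 − 100)/30.44 = 8.7 months at day 100. With viremia, exit = onset + duration + 6 months, up to the cap. Exit is later than Month 12 only if onset + duration exceeds 6 months.

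| Onset (month) | Duration (months) | Exit (month) |
|---|---|---|
| 2 | 2 | 10 |
| 4 | 2 | 12 |
| 6 | 3 | 15 |
| 12 | 6 | 24 |

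A subject who enters directly with viremia at day 100 leaves before Month 12 if viremia clears within 12 − 6 − 100/30.44 = 2.7 months.

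**Step 2: effect on a plain proportion at equal hazard.** Assume the same 10%-per-year hazard in everyone, h = −ln(0.9)/12 = 0.00878 per month, and enrollment at Month 1. The proportion with an event by exit month m is 1 − exp(−h(m − 1)).

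| Exit month | Proportion | Ratio to Month 12 |
|---|---|---|
| 8.5 | 6.4% | 0.69 |
| 10 | 7.6% | 0.83 |
| 12 | 9.2% | 1.00 |
| 18 | 13.9% | 1.51 |
| 24 | 18.3% | 1.99 |

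The ratios change little for hazards from 1% to 20% per year (1.88 to 2.08 at Month 24).

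**Step 3: averaged over viremic subjects.** The documents give no onset or duration distribution. Section 2.1.1 says only that viremia is most often detected in the first six months. Assumptions:
- Enrollment is uniform over Months 0.92 to 3.29 (days 28 to 100).
- 50% to 90% of onsets fall between enrollment and Month 6, and the rest in Months 6 to 12, uniform within each period.
- Duration is exponential.
- The 24-month cap runs from enrollment.
- The 10%-per-year hazard is equal in both groups.

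| Onsets before Month 6 | Median duration (months) | Viremic exits before Month 12 | Ratio of proportions |
|---|---|---|---|
| 50% | 6 | 10% | 1.67 |
| 60% | 6 | 12% | 1.63 |
| 75% | 2 | 34% | 1.20 |
| 90% | 1 | 58% | 1.00 |

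Placing early onsets uniformly in Months 1 to 6, with enrollment at Month 1 and the cap at Month 24 post-transplant, gives 0.96 to 1.54, with 12% to 64% leaving before Month 12.

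**Step 4: absolute size.** For the rows with 60% to 75% of onsets before Month 6, 40 viremic subjects yield about 0.7 to 2 extra expected events. The whole-cohort proportion moves from 8.3% to between 8.5% and 8.8%.

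**The case against.** A reader might infer that viremic subjects will show more events through longer observation alone. The documents do not support this. There is no Month 12 floor for viremic subjects and no stated onset or duration distribution, so the net direction depends on inputs that the reader must supply.

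A reader might also infer that the plan compares clinical outcomes between viremic and non-viremic subjects as plain proportions. Section 8.4 specifies no such comparison. The outcome contrast that it does specify by viremia status is GFR, which uses a repeated-measures model.

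Nor does the equal-hazard ratio describe BKVN. The BKVN proportion is for the whole cohort, viremia is not among its listed logistic factors, and section 2.2.1 says virtually all BKVN patients have viremia. A BKVN contrast by viremia would be largely structural. It also cannot be said that the estimate is incomparable with published rates: section 2.1.1 gives 1% to 10% without follow-up periods.

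These objections stand, and so does the small absolute effect on whole-cohort frequencies. They do not supply a horizon for the BKVN incidence or put time at risk into its risk-factor models. The exploratory survival model in 8.4.3 answers a different question. A further objection bears on the remedy: subjects who leave before Month 12 do so because viremia cleared, so censoring them may be informative.

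**Conclusion.** The gap is real and should be closed. From the documents alone, follow-up differs by viremia status in both directions, BKVN incidence and risk factors are analysed without time at risk, and the clinical outcomes have no named analysis.

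The size is less certain. A side-by-side frequency by viremia status would carry an equal-hazard ratio of about 1.0 to 1.7 (0.96 at the lowest under the alternative timing), usually upward. That rests on the assumed onset, duration and hazard, and it applies to outcomes such as rejection, biopsy, dialysis and death. For BKVN the documents fix neither the size nor the direction of the distortion. The defect there is an undefined period and unequal observation among the subjects in whom nearly all cases arise.

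**What to change.** Change the wording of 8.4.1 and 8.4.2:

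- Estimate BKVN and each 3.2.2 clinical outcome as cumulative incidence from transplant to Month 12, with delayed entry at enrollment. Nobody enters before week 4, so label the estimate as conditional on being event-free then.
- Censor exits before Month 12. Treat death as a competing event, and graft loss too where it is not itself the outcome. State the competing events outcome by outcome.
- Fit BKVN risk factors with the Cox or accelerated failure time models already planned for viremia, in place of logistic regression.
- If outcomes are compared by viremia status, use viremia as a time-dependent exposure, or person-time rates.
- Report events after Month 12 separately, as person-time rates among viremic subjects.
- Add a sensitivity analysis in which subjects who left before Month 12 after clearing viremia are assumed event-free to Month 12.

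The cost is SAP text and modest extra programming on dates already collected. No visit, sample or sample-size change is needed. There are two downsides. Late events in viremic subjects leave the main estimate. Exit on clearance may be informative censoring, which the sensitivity analysis gauges but does not remove.

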8.4.3. Exploratory Endpoints

To investigate the association between the incidence between BK viremia and BK viruria, we will utilize the Fisher's exact test or the large-sample chi-squared test for association whichever is applicable. Time to onset and duration of BK viremia and BK viruria will be analyzed using survival analyses.

Logistic regression will be utilized to determine if other viruses such as CMV, adenovirus, etc. are risk factors for BK viremia. This tool will also be used to determine if selected urinary biomarkers of tubular injury are predictors of BKVN.

To assess the relationship of the time to development of BKVN with the use of immunosuppressive therapy, we will use survival regression analysis with the length of use of immunosuppressive weighted by dose as a predictor variable of interest.

Finally, to examine the reproducibility of the quantitative PCR assays at the participating sites and PCR assays at UAB, we compute the differences in the results and construct a 95% confidence interval for the mean difference. We will also create a Bland-Altman plot which will display the differences and their 95% confidence intervals as a function of the mean readings of the two PCR results.

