3.2.3. Exploratory Endpoints

- Frequency of BK viruria (incidence, time of onset, duration, viral load quantitation by PCR) in subjects with and without BK viremia

- Frequency of CMV, EBV, HHV-6, and adenovirus viremia at multiple time points in subjects with and without BK viremia
- Frequency of CMV and adenovirus viruria at multiple time points in subjects with and without BK viremia
- Results of BK PCR assays performed on matched specimens at the participating sites (local or reference laboratories) and at the UAB Central Laboratory
- Results of urinary biomarkers of tubular injury measured at multiple time points in subjects with and without viremia, including any subjects with BKVN. Potential urinary biomarkers include cystatin C, renin, clusterin, Kim-1, b2-microglobulin, osteopontin, retinol binding protein, and markers of cell apoptosis. Urine biomarkers will not be resulted in real-time.

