4. STUDY DESIGN

The primary objective is to define the natural history of BK viremia in renal or renal-pancreas transplant recipients. In order to understand the natural history of infection, we will measure the time to the development of BK viremia and its correlation with progression to end-organ disease (BKVN or BK hemorrhagic cystitis). Data from this intensive natural history monitoring period will allow for the identification of the types of high-risk patients who might benefit from future studies of therapeutic interventions for BKV infection, when effective therapy becomes available. This will be accomplished by serial quantitative BK DNA measurements by PCR in blood (plasma). It is anticipated that most samples (blood and urine) will be collected during routine standard-of-care clinic visits and will not require extra study visits. Phases of the study can be summarized as follows:

- Subject identification and informed consent. Informed consent should be obtained in the peri-transplant period (between 7 days pre-transplantation [T-7d] and 100 days post-transplantation [T+100 d]).
- Prospective screening for BK viremia. Enrollment and initiation of specimen collection should begin no sooner than 4 weeks after transplantation. Enrollment cannot occur later than 100 days after transplantation. **Subjects will be screened (collection of blood and urine for laboratory studies, including BK PCR) approximately monthly for 6 months (timed from the date of transplantation), then every other month for 6 months. For subjects who remain BKV-negative, screening will terminate approximately 12 months from the date of transplantation.**
- Intensive sampling of subjects identified with BK viremia. Subjects identified with qualifying viremia will be sampled approximately every two weeks until resolution of viremia (defined as PCR negative, or <1000 copies).
Note: Patients who did not participate in the prospective screening phase but are identified with BK viremia by standard-of-care testing may be enrolled, as long as they are still within 90 days of transplantation.
- Post-viremia follow-up. Following resolution of viremia, subjects will be sampled (collection of blood and urine) approximately monthly for 6 months (unless another termination event occurs sooner).

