4.9. Study Visits

The study visits for the screening phase will be every 4 weeks \pm 7 days for 6 months (timed from date of transplantation) and then every 8 weeks \pm 14 days. The study visits during the intensive monitoring period are every 2 weeks \pm 7 days until resolution of BK viremia and then every 4 weeks \pm 7 days for 6 months.

Because the first year following kidney transplantation is challenging for patients, all post-enrollment study visits and visit windows are approximations and may fluctuate with study subject availability.

Events occurring at each study visit are listed in Appendix A.

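### Which samples set other-virus status is undefined in the logistic regression for BK viremia; if any positive sample counts, outcome-dependent and mostly post-onset sampling inflates the association

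*Combined protocol and SAP*

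**What the plan says.** The analysis is one sentence in Section 8.4.3: "Logistic regression will be utilized to determine if other viruses such as CMV, adenovirus, etc. are risk factors" for BK viremia. The endpoint behind it, in Section 3.2.3, is "Frequency of CMV, EBV, HHV-6, and adenovirus viremia at multiple time points in subjects with and without BK viremia", with a parallel endpoint for CMV and adenovirus in urine. Neither place gives an exposure window, a rule that the other virus must come before BK onset, or an allowance for the number of samples.

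The schedule splits by outcome. In screening (Section 4), sampling is "approximately monthly for 6 months (timed from the date of transplantation), then every other month for 6 months". Without qualifying viremia, "surveillance will terminate approximately 12 months after the date of transplantation" (Section 4.2). After onset, "Subjects identified with qualifying viremia will be sampled approximately every two weeks until resolution of viremia" (Section 4), followed by six further monthly visits (Section 4.4). Participation may last up to 24 months (Protocol Summary).

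Specimens for BK and other viruses are taken at visits in every phase (Sections 6.1 to 6.3). Section 7.5 says that the non-BK assays are retrospective but not which specimens will be run. Section 4.2 lets patients already viremic enter the intensive phase directly. Section 7.4 leaves changes of immunosuppression in response to BK viremia to the treating physician. Section 8.4.2 plans Cox or parametric survival models for time to onset, without naming other viruses as covariates.

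**The concern.** A risk factor has to come before the outcome, and exposed and unexposed subjects need an equal chance of having the exposure detected. Here becoming a case changes how often and how long a subject is tested. A subject-level predictor meaning ever positive for CMV, for example, then rises with the number of tests. It also counts infections found after BK onset, some of which may follow from changes in immunosuppression made because of the viremia.

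The study is meant to identify high-risk groups for future therapy (Sections 2.1.1 and 4). A co-infection reported as a risk factor because of visit frequency would mislead that aim. Section 8.4 tests at 5% with no multiplicity adjustment.

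**Working it through.** The plan gives no power, effect size or expected frequency for this analysis, so there is no figure of its own to reproduce. The group sizes used below, 40 viremic and 410 non-viremic, come from the GFR power statement in Section 8.2.1. That statement does reproduce: a difference of 5.9 with SD 10.9 gives power 0.90, as stated.

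**Step 1: samples per subject.** BK-negative: months 1 to 6, 8, 10 and 12, which is 9 if enrolled at month 1 and 7 if enrolled at month 3. Viremic: screening samples up to and including the qualifying one, plus D/2 for D weeks of viremia, plus 6. Onset month and D are assumptions; Section 2.1.1 says only that viremia is mostly detected in the first six months. For enrolment at month 1 and onset at month 3:

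| D (weeks) | Samples | After onset | Ratio to 9 |
|---|---|---|---|
| 4 | 3 + 2 + 6 = 11 | 8 (73%) | 1.2 |
| 12 | 3 + 6 + 6 = 15 | 12 (80%) | 1.7 |
| 24 | 3 + 12 + 6 = 21 | 18 (86%) | 2.3 |

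Over onset months 2 to 6 and D from 4 to 36 weeks, the ratio runs from (2 + 2 + 6)/9 = 1.1 to (6 + 18 + 6)/9 = 3.3. The lowest post-onset share is 8/14 = 57% (onset month 6, D = 4).

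**Step 2: null odds ratio for any positive sample.** With equal per-sample positivity p in both groups and independent samples, P(ever positive) = 1 − (1 − p)^n. The odds ratio against 9 samples is then:

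| p (assumed) | n = 11 | n = 15 | n = 21 |
|---|---|---|---|
| 1% | 1.23 | 1.72 | 2.48 |
| 3% | 1.26 | 1.84 | 2.84 |
| 5% | 1.29 | 1.97 | 3.30 |

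For example, at p = 1% and n = 11: (0.1047/0.8953)/(0.0865/0.9135) = 1.23.

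**Step 3: simulation under no true association.** 40 versus 410 subjects, enrolment at months 1 to 3, onset weighted to months 1 to 6, median viremia 4, 12 or 24 weeks, p = 2% or 5%, likelihood-ratio test at two-sided 5%, 1,500 runs per setting. Mean samples were 13 to 24 in viremic and 8 in BK-negative subjects.

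| Within-subject correlation | Null odds ratio | False-positive rate |
|---|---|---|
| 0, p = 2% | 1.7 to 3.3 | 26 to 87% |
| 0, p = 5% | 1.8 to 4.0 | 45 to 98% |
| 0.1 | 1.4 to 2.2 | 12 to 60% |
| 0.3 | 1.3 to 1.6 | 8 to 21% |

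Steps 2 and 3 together give about 1.2 to 4.0 for independent samples. The effect can be smaller still: with fixed counts of 11 versus 9, correlation 0.3 and p = 10%, the odds ratio was 1.14.

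**Step 4: other definitions of the predictor.**
- Enrolment sample only, in both groups: odds ratio 0.96 to 1.11, rejection 2 to 10%. The spread reflects few positives; at p = 2%, 40 × 0.02 = 0.8 are expected among viremic subjects.
- Same window in both groups (3 versus 3 samples, p = 1 to 10%): rejection 2 to 10%.
- Post-onset samples dropped in cases, full year kept in controls: odds ratio 0.39 to 0.62, rejection 14 to 67%, in the protective direction.
- Per-sample positivity rate (by reasoning, not simulated): no frequency artefact, but post-onset results still count, and the direction of the remaining bias is open.

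**The case against.** A reader might infer that the plan pools all samples and that a false association is therefore built in. The documents do not support that. Section 8.4.3 states neither an ever-positive rule nor an all-samples rule. The wording of Section 3.2.3 can be read as a comparison time point by time point, which does not accumulate with visits. Section 7.5 does not say that every stored specimen will be assayed. With an enrolment-sample predictor the artefact disappears.

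Nor can one say that viremic subjects are always sampled far more often. With four weeks of viremia and onset at month 3 the count is 11 against 9, and the null odds ratio is only 1.2 to 1.3. Repeat samples two weeks apart are unlikely to be independent, and correlation shrinks the effect. The analysis is exploratory, and neither the enrolment target nor the GFR power depends on it.

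All of this stands, and it makes the size conditional. It does not remove the point. Any positive sample is a natural subject-level predictor for an endpoint measured repeatedly, and no rule in the plan restores time order or equal opportunity for detection. The survival models in Section 8.4.2 are only a partial answer, because other viruses are not named there and no time-dependent covariate is specified.

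**Conclusion.** The point holds as a conditional one. The plan leaves other-virus status undefined in a setting where sampling depends on the outcome and most samples of a viremic subject fall after onset. If any positive sample counts, a null association is inflated to an odds ratio of about 1.2 to 4.0 with independent samples, and about 1.3 to 1.6 at within-subject correlation 0.3 in the simulated cohorts. In those cohorts the false-positive rate was above the nominal 5% in every setting.

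These figures rest on assumed per-sample positivity, viremia duration, onset month and correlation, none of which the documents give, and on every collected specimen being assayed. They show what the plan permits, not what it prescribes. The consequence is confined to an exploratory endpoint, but the repair is cheap enough to make before the retrospective assays are analysed.

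**What to change.** In Section 8.4.3, replace the logistic regression for this question with the onset survival model of Section 8.4.2. Use time since transplant, with subjects entering the risk set at enrolment. Enter other-virus status as a time-dependent covariate taken only from samples before the first qualifying BK sample, and state whether it is the latest result or any positive to date. Cases are then compared with subjects still BK-negative at the same time since transplant, on the common screening schedule. This model was not simulated; the nearest check is the equal-window comparison in Step 4.

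A simpler alternative is logistic regression on the enrolment-sample result only. It will have few positives and little power.

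Under either option, exclude from this analysis patients enrolled directly with viremia and subjects viremic at enrolment. This also removes the left-censoring that Section 8.4.2 gives as a reason to leave the Cox model. Do not simply drop post-onset samples in cases while controls keep their full year, because that reverses the bias (null odds ratio about 0.4 to 0.6).

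The cost is SAP wording and no new assays. Post-onset samples, and subjects without a pre-onset sample, are not used for this question; they remain available for the descriptive frequencies in Section 3.2.3.
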